# STUDY PROTOCOL AND STATISTICAL ANALYSIS PLAN

PROJECT TITLE: Mobile Web-based Behavioral Intervention for  
Improving Caregiver Well-being

Date: 9/1/2019

NCT Number: NCT03506945

PROTOCOL ID: 180454

PROJECT TITLE
Mobile web-based behavioral intervention for improving caregiver
PRINCIPAL INVESTIGATOR
[name]
DURATION OF THE STUDY
5 years
LAY LANGUAGE SUMMARY OR SYNOPSIS
Caregivers of persons with dementia suffer great amounts of distress that significantly impacts their mental and physical well-being, and ability to care for the patient at home without resort to nursing home placement. Yet, caregivers' access to quality, evidence-based interventions to assist them is currently very limited. We propose to test the efficacy of a web-based Behavioral Activation intervention called the Pleasant Events Project (mPEP) that has potential to significantly improve caregiver well-being.
SPECIFIC AIMS
Aim 1: Test the efficacy of wBA for improving caregiver well-being.
H1: Caregivers receiving the mPEP intervention will report improved positive affect, reduced negative affect, and improved mental and physical well-being compared to caregivers receiving a web-based bibliotherapy intervention.
Aim 2: Assess mechanisms of the mPEP intervention that promote well-being.
H2: Via data collected in the web-based portal, greater engagement in pleasant activities (i.e., treatment adherence) will be associated with greater improvement of caregiver well-being outcomes.
Aim 3: Assess the influence of the mPEP intervention for promoting physical health.
H3: Caregivers assigned to the mPEP intervention will show greater reduction in blood pressure relative to those assigned to a web-based bibliotherapy intervention.
BACKGROUND AND SIGNIFICANCE
The primary aim of this study is to conduct a stage II randomized clinical trial to test the efficacy of a newly adapted web-based Behavioral Activation treatment called the mobile Pleasant Events Project (mPEP), that can be widely disseminated at low cost and in a convenient manner to caregivers of persons with Alzheimer's Disease and Related Dementias (ADRD). Our lab has demonstrated that a face-to-face version of this intervention is efficacious for promoting well-being in caregivers, and we also have preliminary evidence that the mechanisms associated with the intervention (i.e., greater engagement in pleasant activities) are associated with improved blood pressure in this population. Over 15 million men and women provide informal caregiving services to family members who have dementia. The literature is replete with evidence that caregiving results in high rates of distress, and potentially high rates of physical morbidity. Caregivers consistently report increased distress and reduced well-being relative to their non-caregiving peers, and increased distress is associated with physical health consequences (e.g., cardiovascular disease). Thus, efficacious interventions that are more easily accessible to caregivers are critical for improving mental and physical well-being in this population.
Although much research has been conducted evaluating the efficacy of psychosocial interventions for reducing

distress in this population, caregivers continue to have difficulty accessing these treatments. Currently, most caregiver intervention frameworks require caregivers to meet with a therapist in one of four formats: a) face-to-face meetings with a therapist outside the caregiver's home, b) face-to-face meetings with a therapist in the caregiver's home, c) in-person, group-based meetings (e.g., support groups, group therapy) where the caregiver receives treatment with other caregivers, or d) phone-based interventions in which caregivers call a therapist or support group. While possibly efficacious in reducing caregiver distress, these therapeutic formats are limited because: a) community agencies serving caregivers do not offer Evidence-Based Therapies (EBTs), b) the interventions are often not accessible to caregivers who reside outside the care network, c) they require caregivers to attend therapy sessions on specific days and at specific times that may not be convenient for them, or d) they may require caregivers to find alternate care for their care recipients while they attend the therapy. To address these limitations, we adapted our existing, evidence-based and brief face-to-face Behavioral Activation intervention, into a mobile web application. Our intervention was designed to help caregivers understand factors that contribute to and maintain their distress symptoms and to implement strategies designed to help them create positive, rewarding environments that promote mental and physical well-being. In the newly developed mPEP intervention, caregivers will learn and apply specific behavioral strategies to promote well-being, and be able to receive feedback, on their mobile phones, on how these behavioral strategies are working to promote their well-being. Of particular advantage to the mPEP intervention over other potential intervention adaptations are: a) The theoretical background of behavioral activation is intuitive to end-users, and implementation of the principles of the intervention are simple and straightforward, making it highly scalable and acceptable to both caregivers and community-based organization who may implement it, and b) The ability to capture real-time data allows caregivers and researchers to better understand the mechanisms by which the intervention reduces distress and improves well-being (i.e., behavioral activation). Overall, the current proposal seeks to increase caregivers' access to quality care by demonstrating that our adapted, scalable, evidence-based intervention (i.e., mPEP) is efficacious via delivery through a web-based portal, while simultaneously allowing for better scientific understand of intervention mechanisms.

## RESEARCH DESIGN AND METHODS

### SUBJECTS

**Setting:** Because some CG find it difficult to leave home and find alternate care arrangements for their spouse in order to participate in research, assessments will take place online using the online survey tool Qualtrics. This design increases participation and retention. Further, by bringing the research closer to the real-life circumstances of caregiving, we enhance the study's ecological validity.

**Sample:** The study will enroll 200 participants, with the following inclusion criteria: a) English-speaking; b) at least 40 years of age; c) have access to a web-based device (e.g., computer; smartphone); d) be in-home caregivers of a loved-one with probable Alzheimer's Disease or related dementia (ADRD), e) be living with their care recipients; and f) providing a minimum of 20 hours of care per week. Participants are required to speak English because a) our web-based materials are only available in English, b) we do not have staff or resources to conduct the intervention or assessments in Spanish; and c) assessment tools, surveys, questionnaires or psychological tests are only available in English. Participants will be excluded if: a) the caregiver or AD patient is diagnosed with a terminal illness with a life expectancy of less than 1 year, b) caregivers are cognitively impaired as measured by a brief screen for cognitive functioning; i.e., a Mini Mental State Exam (MMSE) score of <27, c) caregivers are enrolled in another intervention study or are already receiving psychotherapy to improve well-being or reduce distress. The sample will be recruited from: a) the UCSD Alzheimer's Disease Research Center, b) community-based organizations with whom our research team already has well-established relationships (e.g., the San Diego chapter of the Alzheimer's Association; the Southern Caregiver Resource Center); and c) community support groups. Participants will be of varied gender

and ethnicity.

**Assessments:** Outcomes will be collected at 4 times: a) Pre-intervention, b) mid-therapy (3-months), c) post-therapy (6-months), and 6-months post-intervention. Assessment will be completed online via UCSD's Qualtrics Survey software (<https://ucsd.co1.qualtrics.com/ControlPanel/>). Qualtrics offers a high level of security including 256-bit encryption and HIPAA Compliant Certification. The testing will be via the secured UCSD Qualtrics website and the participant will be given a random digit access code and password via e-mail which will not have any identifying information associated with it (including email address) when the survey is completed/returned. Again, to maintain confidentiality, no identifiable information will be included on the assessment survey.

Details of the survey provided to participants are as follows:

## **Measures**

***Blood Pressure:*** Blood pressure will be collected using an Omron HEM 907XL IntelliSense Professional Digital Blood Pressure Monitor sent to participants using US Mail or similar format. Blood pressure will be self-assessed by participants at baseline, 3-, 9-, and 15-months.

The following section details the information to be collected from caregivers via online administration. Further, we detail the specific time-points at which the information will be collected:

***Depressive Symptoms (Primary Outcome):*** Symptoms of depression will be assessed using the Center for Epidemiological Studies Depression Scale—Revised (CESD-R). The CESD-R is a 20-item scale that asks patients to rate the degree to which they have experienced several symptoms of depression over the past week. Scores of  $\geq 16$  correlate highly with a diagnosis of depression. The scale was revised to better reflect the diagnostic criteria of the DSM-5, and the scale continues to good psychometric properties. This scale addresses RFA-AG-18-030, as depressive symptoms is a key well-being outcome in caregivers. This scale will be administered at baseline, 3-, 9-, and 15-months.

***Positive and Negative Affect.*** We will utilize the Positive and Negative Affect Schedule (PANAS) to assess positive (PA) and negative affect (NA). The PANAS contains 20 items assessing PA and NA. Alpha reliability is excellent, ranging from .83-.90 for the PA scale and .85-.90 for NA. This scale addresses RFA-AG-18-030, which lists positive and negative affect as key outcomes to be assessed. This scale will be administered at baseline, 3-, 9-, and 15-months.

***Mental and Physical Well-Being:*** Mental and physical well-being will be assessed using the SF-12 scale, which is a multi-purpose, short form health survey consisting of 12 questions. Test-retest and internal reliability exceed 0.70 in studies of this scale's psychometric properties. The SF-36 also has excellent content, criterion, and predictive validity. This scale will be administered at baseline, 3-, 9-, and 15-months.

***Caregiver Stress:*** Stress will be assessed using the short form of the Zarit Burden Interview (ZBI), which consists of 12 items asking caregivers to rate stress specifically associated with being a caregiver. The has excellent reliability and validity in caregiver populations. Daily stress will be assessed using the Role Overload scale and will be administered via the mPEP program. The Role Overload scale consists of 4 items in which participants are asked to rate the extent to which they feel globally overloaded by life responsibilities. This scale will be administered at baseline, 3-, 9-, and 15-months.

***Care Recipient Functioning.*** We will assess multiple aspects of care recipient (patient) functioning including

cognitive status, problem behaviors, and problems with daily functional tasks (i.e., ADLs and IADLs). To assess patient cognitive functioning, we will utilize the Clinical Dementia Rating (CDR) scale. This scale is administered to the caregiver only, and is a report of the caregivers experience regarding their loved one's cognitive functioning. The CDR will be administered at baseline and 15 months only. ADLs and IADLs will be assessed using the Activities of Daily Living Questionnaire (ADLQ). This scale consists of 28 items, administered to the caregiver, asking about their loved-one's functioning in 6 domains. This scale will be administered at baseline, 3-months, 9-months, and 15-months. Problem behaviors of patients will be assessed using the Revised Memory and Behavior Problem Checklist (RMBPC). This scale will be administered at baseline, 3-months, 9-months, and 15-months.

**Randomization Procedures:** Once the candidate is eligible, willing to participate, and signs our consent form, he/she will be randomly assigned to one of the two intervention groups via a randomization table.

**Interventions:** As described above, participants will be randomized to one of two intervention conditions. Below are descriptions of the two conditions.

a. *Web-based Pleasant Events Project intervention (mPEP)* – The mPEP intervention is designed to be primarily self-administered via mobile technology, with an initial phase-in period whereby caregivers receive phone coaching and check-ins every two weeks. The mPEP intervention is ideographic in nature; accounting for individual differences in the pleasantness of individual activities across caregivers and the impact of such activities on individual well-being states. The overarching theme of the mPEP intervention is that participants have weekly goals for experiencing positive activities and events which, in the parlance of our app, is characterized by “hearts.” Similar to a Fitbit® sports watch, which sets daily goals for steps and helps individuals track progress toward these goals, our participants receive weekly goals for “obtaining hearts”, whereby hearts are assigned to various activities they personally enjoy, and each time they participate in those activities, they achieve a certain number of hearts (i.e., 1-5 hearts/activity). The mPEP app then helps participants visually see their progress toward their weekly hearts goal, which provides motivation to seek out and participate in more activities if needed. The protocol is also programmed to be adaptable and idiographic to each caregiver. That is, if participants achieve a particular week’s hearts goal, but do not see benefit to their moods, the app will use an algorithm to increase the hearts goal for the subsequent week. If individuals do not meet their hearts goal for a week, but achieve mood benefit, the app will adapt and set the next week heart goal slightly lower.

A key element to keep participants engaged in the program is the use of text reminders. Each night, at a time of the participant’s choosing, a text is sent to participants with a hyperlink to their individualized web-portals. Along with the hyperlink is a message asking users to provide an update on their progress toward their goals for the week. In addition, for the first three months of using the mPEP intervention, participants will receive bi-monthly 10-minute “check-in” calls from a coach to answer questions on how to use the web site, problem-solve any barriers to participating in activities, and encourage participants to do their best to achieve their weekly goals. So as not to overburden caregivers, these check-in calls will be scheduled between the coach and caregiver at a time of the caregiver’s choosing. Participants complete a total of three phases in the project, which are (sample screen shots presented in Figure 3):

**Phase 1:** This phase involves self-monitoring activities over the course of one week. This phase is designed to capture activities the participants already engages in (and when), to help increase awareness of how balanced their lives are with regard to self-care activities vs caregiving activities. At the end of each day, participants complete an activity detailing when they woke up, activities they completed throughout the course of the day, and ratings of how enjoyable/pleasant each activity was. Each activity is entered into a personalized calendar so

they can visually see how they spent their day, as well as how many hearts they received from each activity.

**Phases 2 and 3:** These phases involve the selection and engagement in activities designed to promote overall well-being for the caregiver. In Phase 2, the participant completes a mood questionnaire of their positive and negative affect over the previous week. This is designed to provide participants with a baseline assessment of their well-being, on which to track progress as they move through the stages of the application. Following completion of the questionnaire, the participant receives feedback on all activities during phase 1 that were rated

as at least moderately pleasurable (i.e., rated as 3 hearts). Then, the participant will be provided with a structured group of tasks to help identify treatment goals, including: a) select new activities from several life domains (e.g., hobbies) that may increase access to rewarding experiences, and b) create a weekly goal for “hearts” designed to help participants start with achievable activities that are most likely to produce successful attainment of goals. This helps maintain motivation by taking a stepwise goal-setting approach while helping reduce barriers to treatment compliance. During phase 3, participants track their daily engagement in activities, with each participated activity adding to their weekly hearts goal. At the completion of one week of activities, participants again complete their weekly mood questionnaire. Participants then see their weekly accomplishment

s for hearts achieved and overall mood score. The mPEP algorithm then computes the following week’s hearts goal based on hearts achieved and overall mood. Finally, participants

repeat phases 2 and 3 until completion of the program.

**Figure 3.**  
**Screenshots from mPEP.**  
Left = Phase 1 (self-monitoring), Middle = Phase 2 (activity selection); Right = Phase 3, activity tracking.

PEP

You woke up at 6:15 AM. What was your next activity?

[figure not shown]
[figure not shown]
Activity: Eat breakfast

Enter the activity duration or end time

Time  Duration

End time: 7:00 AM

hearts NEXT DAY DONE

*b. Information and Support Intervention* - Participants randomized to this condition will have personalized web access to a comprehensive resource guide containing materials on coping with specific CG stresses (e.g., developing problem-solving skills; managing care receiver problem behaviors; improving communication), and services available for caregivers in San Diego County (i.e., adult day care services; legal services for seniors; respite services). In this intervention, caregivers choose information most relevant to their current circumstances, accessible any time convenient to them. To ensure equivalent contact and support, for the first three months of using this intervention, participants will receive “check-in” calls every two weeks to answer questions on how to use the web site, problem-solve any barriers to participating in activities, and provide information and any referral to services. In addition, participants will receive a unique log-in key associated with their participant identification number, which will allow us to evaluate treatment compliance data and exposure to the treatment information (e.g., information accessed; time spent logged-in). Further, to ensure similarities in treatment delivery, participants will receive nightly text reminders to access and apply information learned at the web-site.

**Screening Procedures:** Screening will occur in person and will consist of a formal screening questionnaire assessing participant eligibility. In addition to the screening questionnaire, participants will be administered the mini-mental state exam (MMSE) to determine cognitive function and eligibility as per our eligibility criteria.

Participants scoring <27 on the MMSE will be informed they are not eligible to participate in the project.

**Statistical Analyses:** All hypotheses will be two-sided at the 0.05 level and intent-to-treat with data included for all subjects completing at least one post-baseline assessment. Data analyses will employ generalized additive mixed models (GAMMs) tailored for longitudinal data. GAMMs allow for potentially nonlinear effects of independent variables on outcomes; the nature of the nonlinearity and degree of smoothness is data-determined for each independent variable. Models will include as covariates variables that differ significantly by condition. We will use Akaike Information Criterion (AIC) to determine covariance structures and variable selection. To control for inflated Type I error rates from multiple testing within each hypothesis, we will use the Westfall-Young step down maxT randomization procedure, which adjusts p-values for significance in multiple comparisons while taking into account the correlation of the outcomes. In this way we can control for an overall family-wise error rate of .05 while achieving more power than Bonferroni adjustments. **Missing Data:** Follow-up data will be obtained on all participants, regardless of treatment completion. We will perform sensitivity analyses for impact of potentially informative missing data via pattern mixture models extended to incorporate random effects. We anticipate 15% dropout between each time point, accounting for an overall (cumulative) dropout rate of 39%.

**Hypothesis testing: Hypothesis 1:** Caregivers receiving mPEP will report reduced depression, improved positive affect, reduced negative affect, and improved well-being compared to caregivers receiving a web-based bibliotherapy intervention. **Dependent Variables:** Depressive Symptoms, Positive and Negative Affect; SF-36 scores. **Independent Variables:** Condition and Time (Baseline, 3-, 9-, and 15-months). **Statistical Analysis:** This hypothesis will use GAMMs. Condition will be entered as a fixed-effect predictor along with time and their interaction. If the smoothed interaction of condition x time is significant at the .05 level (determined by an F test of relevant coefficients in the model) we will test for pairwise differences with Westfall-Young adjusted p values.

**Power Analysis:** Because the mPEP intervention is based upon our in-person version of PEP for caregivers, we anticipate effect sizes to be comparable to those seen in our previous trials. Accordingly, we powered our study based results showing an effect size of 0.4 (small to moderate) in favor of mPEP with an active comparator. Sample size estimates were based on the Hedeker, et al. method for various covariance structures for mixed effects models. For the proposed study, we assumed an autoregressive covariance structure, with a correlation between sequential assessments set at 0.5 based on our previous trial in caregivers. Using this methodology, assuming an alpha level of 0.05, we have a minimum 90% power to detect an effect size of 0.4 with 15% attrition between each time-point (39% cumulative drop-out rate), when there are 100 subjects per each condition.

**Hypothesis 2:** Greater treatment-associated change in behavioral activation will be associated with greater improvement of caregiver well-being outcomes.

**Statistical Analysis:** For this hypothesis, multilevel (mixed) models will be used. To test for mediation, we will utilize the analytic strategy described by Krull and MacKinnon. In this approach, four conditions are tested: a) the relationship between intervention condition and the dependent variables (e.g. Depressive symptoms), b) the relationship between intervention condition and mediator (behavioral activation), c) the relationship between behavioral activation and the outcome, and d) the relationship between intervention condition and outcome after controlling for the proposed mediator. Mediation will be tested using the Monte Carlo Method for Assessing Mediation (MCMM). **Power Analysis:** The proposed study will be powered to detect if treatment-related change in behavioral activation mediates treatment-related change in depressive symptoms. Therefore, power is based upon the strength of both the 'a' path (i.e., mPEP significantly increases behavioral activation relative to our control condition) and 'b' path (i.e., change in behavioral activation is significantly associated with change in depressive symptoms). As per our pilot data, we conservatively estimate a small-to-medium effect ( $r=.20$ ) between mPEP and behavioral activation ( $r=.20$ ) between mPEP and

depressive symptoms, and a medium effect ( $r=.50$ ) between change in behavioral activation and change in depressive symptoms. With  $N = 200$  and alpha of 0.05, we have 81% power to detect a significant mediation effect. These power estimates are based on 15% attrition between time-points (39% overall project attrition).

**Hypothesis 3:** Caregivers assigned to the mPEP intervention will show greater reduction in blood pressure relative to those assigned to a web-based bibliotherapy intervention.

Dependent Variables: Systolic and Diastolic Blood Pressure. Independent Variables: Condition and Time (Baseline, 3-, 9-, and 15-months). Moderator: Age.

**Statistical Analysis:** This hypothesis will be tested using GAMMs. Condition will be entered into the model as a fixed-effect predictor along with time and their interaction. Because age is a known predictor of blood pressure we will enter age as a covariate and moderator of treatment efficacy in analyses. If the smoothed interaction of treatment condition and time is significant at the .05 level (determined by an F test of the relevant coefficients in the model) we will test all pairwise differences with Westfall-Young adjusted p values. **Power Analysis:** Power estimates were calculated using the Hedeker, et al. method for various covariance structures for mixed effects models. For the proposed study, we assumed an autoregressive covariance structure. An estimated correlation of 0.4 was assumed between sequential assessments based on our pilot data. Using this methodology, assuming an alpha level of 0.05 and 200 subjects (100 per treatment arm), and 15% attrition between time-points (39% cumulative dropout across time-points), we have 80% power to detect a small-to-medium effect size of 0.32.

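### The analysis set labelled intent-to-treat omits caregivers with no follow-up assessment, and covariates are chosen from the data; both can be mended by wording, and the measurable harm is small

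*Combined protocol and SAP*

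**What the plan says.** The Statistical Analyses section labels the analysis "intent-to-treat with data included for all subjects completing at least one post-baseline assessment". The models for Hypotheses 1 and 3 take as independent variables "Condition and Time (Baseline, 3-, 9-, and 15-months", so the baseline value is one of the modelled responses.

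Under Missing Data the plan states "Follow-up data will be obtained on all participants, regardless of treatment completion", then "We will perform sensitivity analyses for impact of potentially informative missing data via pattern mixture models". It also expects losses: "We anticipate 15% dropout between each time point", or 39% cumulatively. It does not say that the pattern mixture models use a wider set than the main analysis.

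On covariates it says "Models will include as covariates variables that differ significantly by condition" and "We will use Akaike Information Criterion (AIC) to determine covariance structures and variable selection". It gives no candidate list, no significance level for the between-arm tests and no AIC procedure. Hypothesis 1, which contains the primary outcome (depressive symptoms), names only condition, time and their interaction. Hypothesis 3 does name age in advance, because age predicts blood pressure.

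**The concern.** An intent-to-treat set is fixed by randomisation. This one depends on a later event, completing a follow-up assessment, so the label and the rule disagree. The caregivers left out are the earliest dropouts. Under the rule as written they are also missing from the sensitivity analysis meant to probe informative dropout. At stake are a little precision, possible bias if early loss is selective in different ways in the two arms, and a sensitivity analysis without its most relevant pattern.

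The covariate rule raises a different issue. Reading the between-arm comparison as one of baseline variables, which is the natural reading although the text does not say so, any significant difference after randomisation is a chance imbalance. Selecting on it does not target variables that predict outcome. AIC does look at fit to outcome, but from an unstated pool. So the adjusted model for the primary outcome cannot be written down before the data are seen.

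**Working it through.** **Inputs.** From the documents: 200 caregivers, 100 per arm; two-sided alpha 0.05; 15% loss per interval over three intervals; autoregressive correlation 0.5 and effect 0.4 SD (Hypothesis 1), 0.4 and 0.32 SD (Hypothesis 3). Assumed: the effect is constant at all post-baseline visits and loss is equal in the two arms unless stated.

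**The plan's own figure.** 1 − 0.85³ = 0.386, which rounds to the stated 39%. Expected numbers seen at the four visits are 200, 170, 144.5 and 122.8.

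**Caregivers left out.** 0.15 × 200 = 30 if nobody who misses month 3 returns. The SD is √(200 × 0.15 × 0.85) = 5.05, giving a 95% range of about 20 to 40. If half return at month 9 (assumed), 15 are left out.

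**Power.** These figures come from maximum-likelihood information with baseline means free in each arm. The degrees of freedom of the interaction test are not fixed, because "the nature of the nonlinearity and degree of smoothness is data-determined for each independent variable", so three versions are shown: the average post-baseline difference (1 df), the full condition-by-time test (3 df), and the optimally weighted 1 df contrast.

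| Case | 1 df average, kept → excluded | 3 df | weighted 1 df |
|---|---|---|---|
| Hypothesis 1, 30 excluded | 73.4 → 70.4% | 64.7 → 61.9% | 80.2 → 77.9% |
| Hypothesis 1, 15 excluded | 74.1 → 72.7% | 65.7 → 64.4% | 81.0 → 79.9% |
| Hypothesis 3, 30 excluded | 51 → 48% | 39 → 37% | 56 → 53% |

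For example, the Hypothesis 1 standard error of the average difference is 0.1547 kept and 0.1604 excluded, and Φ(0.4/0.1547 − 1.96) = 0.734. With baseline means constrained equal across arms, the standard error of a constant effect is 0.1125 and power is 94.5% with either set. Only the differences between sets matter here; the levels depend on which test is used.

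**Bias, a what-if.** Suppose that, in one arm only, early loss is related to baseline severity, so that excluded and retained caregivers there differ at baseline by a gap g. With excluded fraction f, excluding them biases visit k by (1 − ρᵏ) × f × g.
- f = 0.15, g = 0.5 SD: 0.0375, 0.0562, 0.0656; average 0.053 SD. The shift is 0.0531/0.1604 = 0.33 standard errors, and type I error is 6.3% (1 df) or 5.7% (3 df).
- f = 0.15, g = 0.25 SD: average 0.027 SD; type I error 5.3% (1 df) or 5.2% (3 df).
- f = 0.075, g = 0.5 SD: average 0.027 SD; type I error 5.3% (1 df).

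A simulation of the first case gave an average bias of 0.0538 SD excluded and 0.0006 SD kept.

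If loss in one arm instead follows the unobserved month-3 score (gap 0.5 SD, so a shift of −0.15 × 0.5 = −0.075):
- Kept: −0.075 × (1 − 0.5²) × (1, 0.5, 0.25) = −0.056, −0.028, −0.014; average −0.033.
- Excluded: −0.0375, 0, 0.0188; average −0.006.

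Neither set is unbiased.

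**Covariates.** At a 0.05 test level (assumed), the imbalance rule selects any given variable in 5% of trials, whether or not it predicts outcome. With 5, 10 or 15 independent candidates (assumed) it selects at least one in 1 − 0.95⁵ = 23%, 1 − 0.95¹⁰ = 40% or 1 − 0.95¹⁵ = 54% of trials. AIC retains a pure-noise 1 df term with probability P(χ²₁ > 2) = 15.7%. Fixed covariates with R² of 0.10 (assumed) move the 1 df power from 73.4% to 73.9%.

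**The case against.** The strongest reply is that little is lost. The set is defined openly in the same sentence as its label, follow-up is promised for everyone, contact is matched across arms (check-in calls every two weeks and nightly texts), and a missing-data sensitivity analysis is planned. Much of this stands. Following everyone regardless of treatment completion does not remove the exclusion, however, because the same paragraph still expects 15% to be lost before the first follow-up.

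A reader might infer that the exclusion biases the trial. The documents do not support that: nothing in them predicts severity-related loss that differs by arm. The rule discontinuing participants with active suicidal thoughts applies to both arms and is not tied to the period before month 3. Nor is the wider set always closer to the truth. When loss follows the unobserved month-3 score, the narrower set has the smaller average bias, partly through cancellation across visits, and is also closer to zero at months 3 and 9.

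On covariates, the 5% selection rate describes the imbalance rule alone. AIC would retain a truly prognostic candidate almost always: about 99.8% of the time at R² of 0.10 with 170 caregivers, by a single-outcome approximation. So it would be wrong to say that the plan adjusts only for chance imbalances. What remains is that the pool of candidates is unstated and noise terms can enter. It would also be wrong to say that no covariate is named: age is, for Hypothesis 3.

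Finally, a set of all caregivers with any outcome value may still fall short of everyone randomised, because the Randomization Procedures do not place the baseline survey before allocation. That is a fair limit on the remedy.

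**Conclusion.** Both points hold as matters of specification, and both are small in measurable effect. The intent-to-treat label contradicts the inclusion rule, with an expected 30 exclusions; that is an expectation and not a ceiling. The precision cost, 3 power points at most, rests on the plan's own dropout and correlation figures, a constant effect and free baseline means. The bias of 0.03 to 0.05 SD, with 30 excluded, is conditional on an assumed one-arm gap of 0.25 to 0.5 SD and is not a forecast.

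The more practical defect is that the pattern mixture analyses, as written, lack the baseline-only pattern. For covariates, the weakness is the absence of a pre-specified adjusted model for Hypothesis 1, and for Hypothesis 3 beyond age. Inflated error is a tempting further inference, but the plan does not show it. Data-determined smoothness and AIC for the covariance structure are not faulted here. This is a cheap improvement and does not threaten the trial's conclusions.

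**What to change.** 1. Analyse all randomised caregivers with any outcome value, as assigned, including those with baseline only. Run the pattern mixture models on that same set, stating the identifying restriction for the baseline-only pattern, which has no follow-up data of its own. Report separately any randomised caregiver with no outcome value.
2. Delete the between-arm significance rule and AIC variable selection. For each hypothesis, name in advance a short list of baseline covariates that the investigators judge prognostic and that are recorded before allocation is disclosed, and use them whatever their balance. Age is already named for Hypothesis 3; the documents do not establish which variables are prognostic for Hypothesis 1, so that choice is the investigators'. AIC may stay for the covariance structure.

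The cost is SAP wording and a few extra fixed parameters, with no new data, visits or participants. Keeping baseline-only caregivers does not cure outcome-related dropout, so the pattern mixture analyses are still needed.
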